8.3.4. Sensitivity Analyses

Multiple sensitivity analyses for the PFS by BICR will be conducted as defined below:

- discounting the event of PD if pleural effusion is the only reason of PD per BICR and the patient is experiencing chylous effusion at the time of PD (see Sensitivity Analysis [SA] 6 [Table JZJB.4](#));
- ignoring new systemic anticancer therapy (see SA2 [Table JZJB.4](#)) according to the EMA guidelines of censoring scheme (EMA 2012);
- using other rules for censoring (as defined by [Table JZJB.4](#));
- using an unstratified logrank test and an unstratified Cox regression model;
- using stratification factors based on the eCRF data;
- repeating the main PFS by BICR analysis for the PP population.

Table JZJB.4. PFS Censoring Scheme - Sensitivity Analyses

Definition	Situation	Event/ Censor	Date of Event or Censor
SA1: Ignoring absence of adequate postbaseline tumor assessment	No adequate postbaseline tumor assessment available and death reported after 2 scan intervals following randomization	Event	Death
SA2: Ignoring new systemic anticancer therapy	New systemic anticancer therapy and: 1. No tumor progression by BICR and no death 2. Tumor progression by BICR or death after start of new therapy	1. Censored 2. Event	1. Date of last adequate tumor assessment, per RECIST 1.1 criteria, or date of randomization (whichever is later) 2. Earliest date of PD or death
SA3: Considering events right after the new systemic anticancer therapy starts	Tumor progression by BICR or death within next 14 days from the start of new systemic anticancer therapy	Event	Earliest date of PD by BICR or death
SA4: Ignoring missing tumor assessments	Tumor progression by BICR or death documented after 2 or more missing scan intervals following last adequate tumor assessment or randomization (whichever is later)	Event	Earliest date of PD by BICR or death
SA5: Considering lost to follow up as tumor progression	Patient lost to follow up and no tumor progression by BICR and no death	Event	Date of next scheduled tumor assessment at or after patient was lost to follow up
SA6: Discounting PD confounded by chylous effusion	Pleural effusion is the only reason of PD per BICR and the patient is experiencing chylous effusion at the time of PD	Censor	Date of last adequate tumor assessment, per RECIST 1.1 criteria

Abbreviations: BICR = blinded independent central review; PD = progressive disease; PFS = progression-free survival; RECIST 1.1 = Response Evaluation Criteria in Solid Tumors, version 1.1; SA = sensitivity analysis.

8.4. Secondary Endpoints Analyses

8.4.1. Key Secondary Endpoints

8.4.1.1. TFFS by BICR

8.4.1.1.1. Research Objective and Question

A secondary research objective and question is: What is the difference in TFFS time between selpercatinib and cabozantinib/vandetanib as the first line therapy in patients with progressive, advanced, kinase inhibitor-naïve, RET-mutant MTC.

8.4.1.1.2. Definition of Endpoint

The estimand for this secondary objective is described by the following attributes:

- Population: patients with progressive, advanced, kinase inhibitor-naïve, RET-mutant MTC. Further details can be found in Protocol Section 5 Study Population.
- Endpoint: treatment failure free survival by BICR, which is defined as the time from randomization to the first occurrence of:
 - documented radiographic disease progression per RECIST 1.1 as assessed by BICR; or
 - unacceptable toxicity leading to treatment discontinuation as assessed by the investigator. To qualify as an event, the toxicity must be from an intolerable AE (defined as any study drug-related AE that meets protocol guidance for treatment discontinuation, with the exception of alopecia); or
 - death (due to any cause).

An independent review committee will review blinded data to determine whether an AE leading to treatment discontinuation meets protocol guidance and thus should be considered as a TFFS event. Independent review will occur retrospectively and will be used in analysis to identify the TFFS events.

- Treatment condition: the randomized study intervention (selpercatinib or cabozantinib/vandetanib) will be administered twice or once a day in continuous 28-day cycles until disease progression, unacceptable toxicity or other protocol-defined reasons for treatment discontinuation. Further details on study interventions including interventions, concomitant therapy and dose modification can be found in Protocol Section 6 Study Intervention.
- Intercurrent-event strategies for main analytical approach are listed in [Table JZJB.5](#).
- Population-level summary measure: hazard ratio of TFFS in selpercatinib versus cabozantinib/vandetanib estimated using a stratified Cox regression model (Cox 1972)

Table JZJB.5. Intercurrent Events of TFFS

Intercurrent Event	IES
Study intervention discontinuation due to reasons other than TFFS event	“Treatment policy” strategy: regardless of whether or not this kind of study intervention discontinuation had occurred
Post study intervention discontinuation anticancer therapy prior to TFFS event	“While on treatment” strategy: consider the assessment of endpoint up until the time that post study intervention discontinuation anticancer therapy is taken
Extended time without adequate assessment prior to TFFS event	“While on treatment” strategy: consider the assessment of endpoint up until the occurrence of extended time without adequate assessment

Abbreviation: IES = intercurrent-event strategies; TFFS = treatment failure-free survival.

Rationale for IES: The interest lies in the treatment effect without the confounding effect of other anticancer therapy or extended time without adequate assessment.

- Study intervention discontinuation due to reasons other than TFFS event is handled with treatment policy as it reflects clinical practice. Time from randomization until disease progression, treatment discontinuation due to unacceptable toxicity or death regardless of other kinds of study intervention discontinuation will be considered in analysis.
- A post study intervention discontinuation anticancer therapy taken prior to TFFS event will confound the treatment effect of selpercatinib in terms of TFFS. If the anticancer therapy is taken, future disease progression/death status is not needed. The participant will be censored and only the time prior to the post study intervention discontinuation anticancer therapy will be considered in analysis.
- TFFS event observed after an extended time without adequate tumor assessment may have occurred much earlier but is not reported because the scheduled assessment was not done. This inadequate observation may introduce bias to TFFS estimates. If extended time without adequate assessment occurs, the participant will be censored and only the time up to the last adequate tumor assessment will be considered in analysis.

8.4.1.1.3. Main Analytical Approach

Since TFFS events include PFS events with additional events of treatment failure due to toxicity, TFFS is sufficiently powered as result of sample size determination based on PFS events.

Conditional on achieving a statistical significance for the primary endpoint of PFS, TFFS by BICR will be tested once at the time of the final analysis which is triggered by the PFS events, in a manner that will preserve the overall Type I error rate at the 1-sided significance level of 0.025 (see Section 8.8 Interim Analyses for details).

- If the study remains at the initial planned total number of PFS events and sample size, the TFFS will be compared between treatment arms using a stratified logrank test, stratified by the 2 randomization strata based on IWRS data: RET mutation (M918T vs. other) and intended control treatment (cabozantinib vs. vandetanib).
- If the total number of PFS events required for the final analysis increases after sample size re-estimation, the TFFS will be compared between treatment arms using the CHW test in a similar manner of the primary efficacy analysis:

Table JZJB.6. Defining the Values for Computing the CHW Test Statistic of TFFS

Quantity	Input Value or Derivation / Calculation
$Z_{TFFS,1}$	This is the stratified logrank test statistic comparing TFFS between treatment arms at the interim analysis. The interim analysis is triggered after approximately 56 PFS events have occurred (at 75% PFS information fraction).
$Z_{TFFS,2}$	This is the stratified logrank test statistic comparing TFFS between treatment arms at the final analysis.
$e_{TFFS,1}$	This is the observed number of TFFS events across both treatment arms at the interim analysis.
$e_{TFFS,2}$	This is the number of TFFS events across both treatment arms at the final analysis should the study remain at the initial planned 74 total number of PFS events. This number is projected to be 88 assuming a median TFFS of 20 months for Arm B (Wells et al. 2012) and HR of 0.5. $e_{TFFS,2} = 88$
$e_{TFFS,2}^*$	This is the observed number of TFFS events across both treatment arms at the final analysis.

Given the quantities defined in Table JZJB.6, the final CHW test statistic for the TFFS analysis can be written as:

$$Z_{TFFS,CHW} = \sqrt{\frac{e_{TFFS,1}}{e_{TFFS,2}}} Z_{TFFS,1} + \sqrt{\frac{e_{TFFS,2} - e_{TFFS,1}}{e_{TFFS,2}}} \left\{ \frac{\sqrt{e_{TFFS,2}^*} Z_{TFFS,2} - \sqrt{e_{TFFS,1}} Z_{TFFS,1}}{\sqrt{e_{TFFS,2}^* - e_{TFFS,1}}} \right\}$$

- ^b Adequate tumor assessment per RECIST 1.1 criteria refers to an assessment with 1 of the following responses: CR, PR, SD, or PD.
- ^c The 2-scan interval is counted from the date of the last adequate tumor assessment to the date of the next 2 scheduled tumor assessments plus 14 days (adjusted by tumor assessment window).
- If there are multiple dates associated with 1 assessment, the assessment date will be set to the first date when the overall response is PD and the last date otherwise.

8.4.1.1.4. Sensitivity Analyses

Multiple sensitivity analyses for the TFFS will be conducted as defined below:

- counting the time of the third dose reduction due to hypersensitivity, hepatic lab abnormalities, or QT interval corrected for heart rate using Fridericia's formula (QTcF) > 500 msec as the TFFS event for patients on Arm A who continue treatment after > 2 dose reductions (see SA1 in [Table JZJB.8](#));
- ignoring new systemic anticancer therapy (see SA5 [Table JZJB.8](#)) according to the EMA guidelines of censoring scheme (EMA 2012);
- discounting the event of PD if pleural effusion is the only reason of PD per BICR and the patient is experiencing chylous effusion at the time of PD (see SA7 [Table JZJB.8](#));

- using other rules for censoring (as defined by [Table JZJB.8](#));
- using an unstratified logrank test and an unstratified Cox regression model;
- using stratification factors based on the eCRF data;
- repeating the main TFFS analysis for the PP population.

Table JZJB.8. TFFS Censoring Scheme - Sensitivity Analysis

Definition	Situation	Event/ Censor	Date of Event or Censor
SA1: Counting the third dose reduction due to hypersensitivity, hepatic lab abnormalities, or QTcF >500 msec as treatment discontinuation	The third dose reduction due to hypersensitivity, hepatic lab abnormalities, or QTcF >500 msec for patients on Arm A who continue treatment after >2 dose reductions	Event	Date of the third dose reduction
SA2: Ignoring absence of adequate postbaseline tumor assessment	No adequate postbaseline tumor assessment available and death reported after 2 scan intervals following randomization	Event	Earliest date of symptomatic deterioration or death
SA3: Ignoring missing tumor assessments	Tumor progression by BICR or death documented after 2 or more missing scan intervals following last adequate tumor assessment or randomization (whichever is later)	Event	Earliest date of PD by BICR or death
SA4: Considering lost to follow up as tumor progression	Patient lost to follow up and no tumor progression by BICR and no death	Event	Date of next scheduled tumor assessment at or after patient was lost to follow up
SA5: Ignoring new systemic anticancer therapy	New systemic anticancer therapy and: 1. No tumor progression by BICR and no death 2. Tumor progression by BICR or death after start of new therapy	1. Censored 2. Event	1. Date of last adequate tumor assessment, per RECIST 1.1 criteria, or date of randomization (whichever is later) 2. Earliest date of PD or death
SA6: Considering events right after the new systemic anticancer therapy starts	Tumor progression by BICR or death within next 14 days from the start of new systemic anticancer therapy	Event	Earliest date of PD by BICR or death
SA7: Discounting PD confounded by chylous effusion	Pleural effusion is the only reason of PD per BICR and the patient is experiencing chylous effusion at the time of PD	Censored	Date of last adequate tumor assessment, per RECIST 1.1 criteria

Abbreviations: BICR = blinded independent central review; PD = progressive disease; QTcF = QT interval corrected for heart rate using Fridericia's formula; RECIST 1.1 = Response Evaluation Criteria in Solid Tumors, version 1.1; SA = sensitivity analysis; TFFS = treatment failure-free survival.

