6.6. Dose Modification

Intolerable AEs that lead to treatment discontinuation (except alopecia) will meet criteria to be included in the TFFS endpoint. Intolerable AEs are defined as any study drug-related AE that meets protocol guidance for treatment discontinuation.

- Permanently discontinue treatment for any of:
 - Cabozantinib: development of visceral perforation or fistula formation, severe hemorrhage, serious arterial thromboembolic event (e.g., myocardial infarction, cerebral infarction), nephrotic syndrome, malignant hypertension, hypertensive crisis, persistent uncontrolled hypertension despite optimal medical management, osteonecrosis of the jaw, reversible posterior leukoencephalopathy syndrome
 - Vandetanib: development of prolonged QT interval not improved with electrolyte correction and/or dose reduction, severe skin reactions, ILD, ischemic cerebrovascular events, hemorrhage, heart failure, persistent uncontrolled hypertension despite optimal medical management, or reversible posterior leukoencephalopathy syndrome
 - Selpercatinib: malignant hypertension, hypertensive crisis, persistent uncontrolled hypertension despite optimal medical management, or severe/life-threatening hemorrhage. Patients with clinical benefit who experience recurrent hypersensitivity reaction or recurrent AST or ALT increase despite dose reductions should be

discussed with the Lilly medical team and may be allowed to continue treatment with more than 2 dose reductions if continuation is considered to be safe and in their best interest

Dose reductions should be made according to the following parameters using the dose reduction table below. Interrupt dosing for CTCAE v5.0 Grade 3 or greater AEs or Grade 2 AEs not resolved within 48 hours with appropriate supportive care (e.g., nausea not improved with antiemetics) and considered intolerable by the patient or the investigator.

- For selpercatinib related hypersensitivity, liver function test abnormalities, thrombocytopenia, and hypertension, see dose adjustments below in Sections 6.6.1, 6.6.2, 6.6.3, and 6.6.4, respectively.
- Regardless of treatment arm, study treatment may continue for hypertension that is considered Grade 3 on the basis of requiring ≥ 2 anti-hypertensives or more intensive anti-hypertensive therapy than baseline once blood pressure is stabilized.

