- Dose modifications for ECG changes are described in Section 8.2.1. If a patient receiving selpercatinib or cabozantinib experiences QTcF > 500 msec despite 2 dose reductions and if the investigator deems it in the best interest of the patient, the patient may continue treatment with study drug with Lilly medical approval. In addition, Lilly will request a copy of the ECGs for adjudication.
- Upon resolution (or return to patient's baseline) of AEs at least possibly related to treatment, reduce the dose as follows:
 - If previously receiving dose level 1, resume treatment at dose level -1
 - If previous receiving dose level -1, resume treatment at dose level -2
 - If previously receiving dose level -2, resume treatment at the same dose level. If a second AE requiring dose modification occurs at dose level -2, discontinue study treatment.
 - For AEs clearly unrelated to study treatment that resolve or return to patient's baseline in ≤ 14 days, dose reduction is not required.
 - Re-escalation to a prior dose level after a dose reduction is permitted once the AE requiring dose reduction is resolved. See Sections 6.6.1 through 6.6.4 and the IB for specific dose adjustments required for patients receiving selpercatinib.
 - Above are guidelines and may be superseded by local practice guidelines or advice per the local cabozantinib/vandetanib labels when appropriate.

Except as noted, a maximum of 2 dose level reductions will be allowed. Any patient requiring > 42 days omission of treatment for drug-related toxicities will meet the criteria for study treatment discontinuation. Treatment omissions of > 42 days in extenuating circumstances that are not drug-related (e.g. recovery from motor vehicle accident) may be approved by the Lilly medical team.

General Dose Reductions for Treatment Related Toxicities^a

| Dose Level | Time | Selpercatinib Dose (mg) | Cabozantinib Dose (mg) ^b | Vandetanib Dose (mg) |
|---------------|------|-------------------------|-------------------------------------|----------------------|
| Dose Level 1 | AM | 160 | 140 | 300 |
| | PM | 160 | - | - |
| Dose Level -1 | AM | 120 | 100 | 200 |
| | PM | 120 | - | - |
| Dose Level -2 | AM | 80 | 60 | 100 |
| | PM | 80 | - | - |

^a Unless other specific dose reductions, as per Sections 6.6.1, 6.6.2, 6.6.3, and 6.6.4.

In the instance that vandetanib 100-mg tablets are unavailable, but vandetanib 300-mg tablets are available, the below table is to be followed in adult patients.

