6.6.1. Dose Modifications for Selpercatinib Hypersensitivity

If selpercatinib drug hypersensitivity is suspected, study drug should be held and treatment with steroids at 1 mg/kg prednisone (or equivalent) should be initiated. Upon resolution, selpercatinib may be resumed at a reduced dose of 40 mg BID (or adolescent equivalent dose) while continuing steroids at the same dose. Note that this dose reduction does not require sponsor approval. Hypersensitivity has recurred in some patients, typically at 3 to 6 hours following drug administration.

Discontinue selpercatinib for recurrent clinically significant hypersensitivity. In the absence of clinically significant recurrent drug hypersensitivity, the dose of selpercatinib may be escalated sequentially to 80 mg BID, 120 mg BID, and 160 mg BID (or adolescent equivalent doses) for a minimum of 7 days at each dose. Once the patient has tolerated treatment for a minimum of 7 days at the final dose, steroids may be tapered slowly.

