6.6.2. Dose Modifications for Selpercatinib Related Liver Test Abnormalities

If a patient experiences Grade ≥ 3 elevated hepatic lab increases (ALT, AST, or direct bilirubin), study drug should be held and evaluation for potential alternative causes should be conducted (e.g., history of other hepatotoxic medications/substances, viral serologies, liver imaging). The grading is according to Common Terminology Criteria for Adverse Events (CTCAE) version 5.0 with slight modification as described in Section 8.3. A repeat value 3 to 5 days after the initial finding of elevation of labs should be obtained to confirm the abnormality and to confirm if it is increasing or decreasing. Thereafter, hepatic labs should be monitored at least weekly until resolution to normal/baseline (depending on the clinical situation, resolution to Grade 1 if baseline is normal may be acceptable but awaiting normalization is preferable. If the abnormalities do not begin to resolve (or worsen) within 5 days of the AE, a hepatology consultation should be considered to evaluate the need for a liver biopsy. Due to the question of a

possible immune component to the lab abnormalities observed, some patients with persistent increases have initiated treatment with steroids, with subsequent improvement.

Upon resolution, selpercatinib may be resumed at a reduced dose of 2 dose levels lower than at which the abnormalities occurred with weekly lab monitoring. In the absence of recurrent abnormalities, the dose of selpercatinib may be escalated sequentially to the next higher dose level after a minimum of 2 weeks at the lowest dose level, and again to the dose level at which the abnormalities occurred after a minimum of 4 weeks at the dose level below which the abnormalities occurred. Once the patient has been treated at a stable dose of selpercatinib for a minimum of 4 weeks without recurrent lab abnormalities, the frequency of monitoring may be decreased (e.g., every 2 weeks for 2 months and then monthly thereafter). For patients who experience Grade ≥ 3 elevated hepatic labs on a dose of 80 mg BID (or adolescent equivalent dose), the Lilly medical team should be contacted for additional guidance to determine if continuation with dose modification is acceptable. If the patient experiences \geq Grade 3 elevated ALT, AST, or direct bilirubin at a dose of 40 mg BID, selpercatinib should be discontinued.

Please refer to Section 8.2.2. for additional monitoring that may need to be initiated.

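### TFFS sensitivity analysis SA1 fires on the third dose reduction, which does not reliably identify the Arm A patients kept on treatment under the protocol's exemptions

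*SAP*

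**What the plan says.** **SAP.** Table JZJB.8 in 8.4.1.1.4 makes the following an SA1 event, dated at the third reduction: "The third dose reduction due to hypersensitivity, hepatic lab abnormalities, or QTcF >500 msec for patients on Arm A" who continue after more than two reductions. The SAP does not say whether a dose reduction means an occasion of lowering the dose or a step on the dose table.

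**Protocol, general limit (6.6).** The limit is in levels: "Except as noted, a maximum of 2 dose level reductions will be allowed". The lowest adult row is "Dose Level -2 | AM | 80 | 60 | 100", so selpercatinib Level -2 is 80 mg BID. A patient at Level -2 resumes at the same level after a first adverse event; a second one needing dose modification means discontinuation. Re-escalation is permitted after resolution. Protocol 4.1 words the limit as two dose reductions, without the word level.

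**Protocol, exemptions and special paths.**
- Recurrent hypersensitivity or transaminase increase on selpercatinib (6.6): the patient "may be allowed to continue treatment with more than 2 dose reductions if continuation is considered to be safe".
- QTcF (6.6): "If a patient receiving selpercatinib or cabozantinib experiences QTcF > 500 msec despite 2 dose reductions", treatment may continue with sponsor medical approval. Section 8.2.1 asks for at least a one-level reduction on Arm A.
- Hepatic (6.6.2): "selpercatinib may be resumed at a reduced dose of 2 dose levels lower than at which the abnormalities occurred". For a Grade 3 or higher event at 80 mg BID, the sponsor advises whether continuing with a modified dose is acceptable. At 40 mg BID the drug is stopped.
- Hypersensitivity (6.6.1): "selpercatinib may be resumed at a reduced dose of 40 mg BID (or adolescent equivalent dose) while continuing steroids at the same dose". No sponsor approval is needed for this step. Section 6.6.1 also says to stop for clinically significant recurrence.

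**The concern.** TFFS by BICR is a type I error-controlled key secondary endpoint. Its toxicity component requires a drug-related adverse event that leads to discontinuation and meets the protocol's discontinuation guidance (SAP 8.4.1.1.2). A patient continued under an exemption therefore has no toxicity event at that time, and any TFFS event comes later from progression, death or a later stop.

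SA1 is the only planned analysis that probes this. SA2 to SA7 deal with missing assessments, loss to follow-up, new therapy and chylous effusion. Investigator-assessed TFFS (SAP 8.4.2) drops the guidance condition but still needs an actual discontinuation.

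If the trigger is not tied to use of an exemption, a reassuring SA1 result is hard to interpret. It could mean that few patients were exempted, or that exempted patients did not reach a third reduction.

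**Working it through.** **Inputs.** Adult selpercatinib doses in mg BID: 160 (Level 1), 120 (Level -1), 80 (Level -2) from the 6.6 table, and 40 from 6.6.1 and 6.6.2. The 40 mg dose is one 40 mg step below Level -2 and has no number in the adult table. Step sizes: to 40 mg for hypersensitivity (6.6.1), two levels for hepatic events (6.6.2), one level for QTcF (the minimum in 8.2.1). Assumption: after a hepatic event at 80 mg, the approved modification is 80 to 40.

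**The protocol's own limit.** 160 to 120 to 80 is two reductions and two levels. On one-level steps the count and the depth agree, and a third reduction is the first step below Level -2.

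**The paths SA1 names**, with SA1 read as a count:

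| Path | Reductions | Steps below 160 at lowest dose | SA1 event |
|---|---|---|---|
| Hepatic, 160→80→40 | 2 | 2 + 1 = 3 | none |
| Earlier one-level reduction, then hepatic, 160→120→40 | 2 | 1 + 2 = 3 | none |
| Hypersensitivity, first restart, 160→40 | 1 | 3 | none |
| QTcF, 160→120→80, continues at 80 by exemption | 2 | 2 | none |
| QTcF, 160→120→80→40 | 3 | 3 | yes |
| QTcF, 160→120 three times with re-escalation | 3 | 1 | yes |
| Hepatic, 160→80 three times with re-escalation | 3 | 2 | yes |

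An enumeration of all single-cause paths on this ladder gives the same picture:
- The fewest reductions needed to go below 80 mg BID are 1 for hypersensitivity, 2 for hepatic events and 3 for QTcF.
- Without re-escalation, a third reduction cannot occur on hypersensitivity alone or hepatic events alone. It can on QTcF.
- With re-escalation, hepatic and QTcF patients can have a third reduction without ever going below 80 mg BID.

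**Which rows matter.** Row 1 is a patient continued below Level -2 at sponsor discretion with no SA1 event. Row 4 becomes a miss once the patient has the event at Level -2 that would end treatment under the general rule and continues by exemption without a further reduction. Rows 6 and 7 are SA1 events although, counted in levels, the limit was not passed. Row 3 follows a written path and uses no exemption. Row 5 is captured correctly.

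**The case against.** The strongest reply is that SA1 uses the same unit as the exemptions. Both exemptions in 6.6 speak of two or more dose reductions, as does the limit in 4.1; the general limit in 6.6 speaks of levels. Third dose reduction might also be meant as third level. This stands in part: the wording is ambiguous rather than plainly wrong. A level reading, however, still gives no date to a patient who continues at 80 mg under the QTcF exemption.

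Four stronger readings are tempting, and the documents do not support them:

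- **That the first 40 mg BID restart after hypersensitivity is a hidden failure.** The limit applies except as noted, 6.6.1 writes this step in without sponsor approval, and the dose may later return to 160 mg BID. The patient neither discontinued nor used an exemption.
- **That the hepatic path hides a failure altogether.** The stop at 40 mg BID is protocol guidance, so if drug-related it can already be a TFFS event in the main analysis. What SA1 misses is the earlier date, or the patient who stays at 40 mg.
- **That every QTcF patient escapes.** Section 8.2.1 makes a third one-level reduction realistic, and SA1 then works. Reaching 80 mg and resuming there after a first event is within the general rule.
- **That limiting SA1 to Arm A favours selpercatinib.** It can add events only to Arm A, so it works against selpercatinib. What remains is an inconsistency, because cabozantinib shares the QTcF exemption.

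**Conclusion.** The point holds in limited form. SA1's trigger, read as a count, is incomplete for hepatic and QTcF continuations and can also capture re-escalated patients who never passed the limit in levels. The hepatic part assumes hepatic events alone, no re-escalation, and 80 to 40 mg BID as the approved modification. The QTcF part rests on the exemption not explicitly requiring a third reduction.

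A reader might infer that SA1 will barely move whatever the true effect of the exemptions. That does not follow: SA1 captures stepwise QTcF reductions and repeat reductions after re-escalation, and the documents give no rates for any path. The number of patients affected cannot be computed.

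The consequence is confined to one sensitivity analysis of a key secondary endpoint. The main TFFS test, its alpha and the primary PFS analysis are untouched. The change is still worth making, because no other planned analysis examines the exemptions.

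**What to change.** Redefine the SA1 event as the date on which a patient has a listed event (recurrent hypersensitivity, hepatic laboratory abnormality, or QTcF above 500 msec) at which the general 6.6 limit, counted in dose levels, would require discontinuation, but continues under an exemption or sponsor approval, whether or not the dose is reduced again. State that the first 40 mg BID hypersensitivity restart under 6.6.1 is not an event.

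Keep the Arm A-only analysis as the conservative version. Add a second version applying the same rule to cabozantinib patients who continue under the shared QTcF exemption. It adds Arm B events, so its net direction is unknown in advance.

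Two protocol inconsistencies must be reconciled by the sponsor, and no dosing rule is proposed here: 6.6 and 6.6.1 differ on continuing after recurrent hypersensitivity, and 4.1 and 6.6 differ on dose reductions versus dose level reductions.

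The cost is SAP wording and a small programming change on dose and adverse event data already collected.
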